- Provision of adequate study oversight by personally conducting or supervising the investigation, including, but not limited to: allotting sufficient time to properly conduct and complete the study within the agreed upon time period; having available an adequate number of qualified staff and adequate facilities for the expected duration of the study and to conduct the study properly and safely; and ensuring that all persons assisting with the study are adequately informed about the protocol and the investigational product(s) and are capable of performing their study-related duties and functions. Qualifications of individuals assigned responsibility for the administration of the investigational product will be compliant with state and local law or national regulations, as applicable
- Maintenance of accurate source records from which case report forms are completed as well as drug accountability records that show the receipt and disposition (on an overall and per subject basis) of all study drug(s) shipped to the Investigator by Panoptes Pharma GesmbH

[figure not shown]
In addition, I agree to provide all the information requested in the electronic case report form (eCRF) presented to me by Panoptes Pharma GesmbH by carefully following the completion guidelines provided as part of the eCRF.

If I opt to terminate my participation in the study, the foregoing shall equally apply.

[name]. [name]

Investigator's Name (Please Print)

Investigator's Signature

01/04/2021

Date

SYNOPSIS

Study Title: A phase I safety and tolerability study of PP-001 eye drops in healthy adult volunteers (Protocol PP-001-1101)

Study Objectives:

Primary Objective

The primary objective is to assess the safety and tolerability of 1 day (single dose) and 12 days (48 doses) dosing with ascending doses (0.05% [0.5 mg/mL], 0.15% [1.5 mg/mL] and 0.3% [3.0 mg/mL]) of PP-001 eye drops compared to placebo eye drops in healthy subjects (cohorts 1-3). In addition, safety and tolerability will be tested in a group of 21 patients with ocular surface inflammation (cohort 4).

Secondary Objectives

- To assess the pharmacokinetics of PP-001 eye drops following 1 day (single dose) and 12 days (48 doses) dosing in healthy subjects
- To assess the pharmacodynamics, in relation to the eye, of PP-001 eye drops following 1 day (single dose) and 12 days (48 doses) dosing in healthy subjects and following 12 days (24 doses) dosing in patients with ocular surface inflammation. The following procedures will be used to assess the pharmacodynamics with respect to the eye: Best corrected visual acuity, visual field, intraocular pressure, slit lamp examination, dilated fundoscopy, fundus photography (cohorts 1-3 only), amsler grid.

Study Population:

Inclusion Criteria

Cohorts 1-3:

1. Male or female healthy volunteers 18–64 years of age.
2. Good general state of health (mentally and physically). Laboratory parameters and vital signs of subjects must be within the normal ranges (or judged as not clinically significant by the investigator) and subjects must not have a diagnosis of any eye disease that could affect the pharmacokinetics of PP-001.
3. Willing to provide a signed and dated written informed consent form.
4. Female subjects of childbearing potential must have a negative urine pregnancy test prior to the first administration on Day 0.

5. Male and female subjects must ensure that one highly effective method of contraception, combined with an acceptable method of contraception, is used for the entire duration of the study, from first dose up to the study follow-up visit. Subjects must agree to refrain from becoming pregnant or fathering a child in the 3 months following the last study drug administration. Male subjects must agree with their female partners, prior to screening, to use the above specified methods of contraception while receiving investigational product (IP), and for 3 months after stopping IP.
6. Best-corrected visual acuity of 0.1 log minimal angle of resolution or better in both eyes (approximately 20/25 or better).
7. Intraocular pressure <21 mmHg with differences between eyes of <4 mmHg.

Cohort 4:

1. Male or female subjects 18–64 years of age with ocular surface inflammation in both eyes as defined below.
2. Ocular surface inflammation defined as an Ocular Surface Disease Index (OSDI) of 22 or more AND conjunctival hyperemia of Grade 2 on the Efron Scale or more in both eyes
3. Good general state of health (mentally and physically). Laboratory parameters and vital signs of subjects must be within the normal ranges (or judged as not clinically significant by the investigator) and subjects must not have a diagnosis of any eye disease except ocular surface inflammation.
4. Willing to provide a signed and dated written informed consent form.
5. Female subjects of childbearing potential must have a negative urine pregnancy test prior to the first administration
6. Male and female subjects must ensure that one highly effective method of contraception, combined with an acceptable method of contraception, is used for the entire duration of the study, from first dose up to the study follow-up visit. Subjects must agree to refrain from becoming pregnant or fathering a child in the 3 months following the last study drug administration. Male subjects must agree with their female partners, prior to screening, to use the above specified methods of contraception while receiving IP, and for 3 months after stopping IP.
7. Best-corrected visual acuity of 0.1 log minimal angle of resolution or better in both eyes (approximately 20/25 or better).
8. Intraocular pressure <21 mmHg with differences between eyes of <4 mmHg.

Exclusion Criteria

Cohorts 1-3:

1. Participation in other IP or device clinical trials within 30 days prior to Day 0, or planning to participate in other IP or device clinical trials within 60 days following Day 0. This includes both ocular and non-ocular clinical trials.
2. Female subjects who are pregnant, nursing, or planning a pregnancy, or who are of childbearing potential and not willing to use reliable means of contraception.
3. Subjects with a known allergy or hypersensitivity to the study medication, any component of the delivery vehicle, any corticosteroids or any diagnostic agents used during the study (e.g., fluorescein, dilation drops, antibiotic drops, povidone).
4. Subjects who have used regularly any ocular agents within 60 days prior to Day 0.

Cohort 4:

1. Participation in other IP or device clinical trials within 30 days prior to Day 0, or planning to participate in other IP or device clinical trials within 60 days following the first study day. This includes both ocular and non-ocular clinical trials.
2. Female subjects who are pregnant, nursing, or planning a pregnancy, or who are of childbearing potential and not willing to use reliable means of contraception.
3. Subjects with a known allergy or hypersensitivity to the study medication, any component of the delivery vehicle, any corticosteroids or any diagnostic agents used during the study (e.g., fluorescein, dilation drops, antibiotic drops, povidone).
4. Subjects who have regularly used any ocular agents within 60 days prior to Day 0 except topical lubricants.

Duration of Study: total duration of study for each subject will be 30 days or more (from screening to last follow-up) in cohorts 1-3 and 22 days or more (from screening to last follow-up) in cohort 4.

Drug Products: PP-001 will be supplied as a ready to use eye drop bottle.

Study Drug Assignment: subjects will be dosed in ascending order with 0.05%, 0.15% and 0.30% PP-001 eye drops depending on the cohort to which they are assigned (cohorts 1-3). Subjects in cohort 4 will be dosed with 0.15% PP-001 eyedrops.

Duration of Treatment: subjects will receive up to four eye drops of PP-001 per day in a randomly assigned eye (cohorts 1-3: 4 drops; cohort 4: 2 drops). Subjects will be treated initially for 1 day (Day 0) and then for 12 days (Days 8–19) in cohorts 1-3 and for 12 consecutive days (Days 0-11) in cohort 4.

Study Drug Administration: PP-001 will be instilled up to four times per day as PP-001 eye drops either by the site staff (MD investigator) or by self-administration.

Blinding: this study is double-blinded within each cohort, the subjects and the investigators do not know if the subject will receive placebo or study drug.

Study Design: this prospective, single-centre, double-blind, placebo-controlled, randomised, parallel-group study will be conducted in accordance with the European Union Clinical Trial Directive 2001/20/EC and 2005/28/EC, the Declaration of Helsinki (revised version of Fortaleza, Brazil 2013), Good Manufacturing Practice, Good Clinical Practice and the current national regulations and guidelines. It will be approved by both the local ethics committee and regulatory authority prior to the first subject being screened.

A total of 24 healthy subjects aged between 18 and 64 years will be included into the first three cohorts of eight subjects each. Each cohort will be performed in two parts. In the first part, subjects will be randomized to receive a single dose of PP-001 or placebo. If safety and tolerability is acceptable, subjects will move on to Part II, where subjects will receive PP-001 or placebo according to the randomization in Part I four times a day for 12 consecutive days. If safety and tolerability is demonstrated in Part II, dose escalation will occur in the next cohort.

- In Cohort 1 six subjects will receive four drops of 0.05% (w/v) PP-001 in only one eye and two subjects will receive placebo in only one eye
- In Cohort 2 six subjects will receive four drops of 0.15% (w/v) PP-001 in only one eye and two subjects will receive placebo in only one eye
- In Cohort 3 six subjects will receive four drops of 0.30% (w/v) PP-001 in only one eye and two subjects will receive placebo in only one eye

Cohorts 1 to 3 will be performed in dose ascending order. On the first two study days in Part I of each cohort, one subject will be dosed per day. On the third study day up to two subjects can be dosed per day. On the following study day(s) up to 4 subjects can be dosed per day. Randomization will be performed in two blocks (3:1, PP-001 vs. placebo) for each cohort. Part II will start at least 7 days after the last subject has been dosed in Part I and the Principal Investigator and the sponsor decide whether or not to continue dosing the cohort in Part II. Within each cohort neither subject nor investigator knows if the subject receives placebo or PP-001. A data safety monitoring board will decide if the safety and tolerability demonstrated in Parts I and II of the previous cohort warrant continuing the study at the next highest dose.

In Cohort 4, twenty-one (21) subjects aged between 18 and 64 years with diagnosed ocular surface inflammation will be included. Subjects will receive half of the highest dose that was considered safe by the DSMB based on the safety data of cohorts 1-3. This cohort will be performed in one part (multiple instillations). Subject will receive two daily instillations for 12 consecutive days (in total 24 administrations). Out of 21 subjects, 14 subjects will receive PP-001 eye drops and 7 subjects will receive placebo. A data safety monitoring board will be installed for safety monitoring of cohort 4.

Statistical Considerations:

Sample Size for cohorts 1-3: Twenty-four (24) healthy female or male subjects will be enrolled in the study. No power calculations have been performed and the sample size is based on the requirements of the study design.

Sample Size for cohort 4: Twenty-one (21) subjects with diagnosed ocular surface inflammation will be treated. No power calculations have been performed and the sample size is based on the requirements of the study design.

Treatment Comparison of Interest: a comparison will be made between the cohorts with regard to safety and tolerability.

Analysis Populations

- *Intent-to-treat (ITT) Analysis Set:* all subjects regardless of whether or not the subject received study drug
- *Per-protocol Analysis Set:* all ITT Analysis Set subjects who have no major protocol deviations and who complete the study up to the end of the post-study assessments
- *Safety Analysis Set:* all subjects who receive any amount of study drug. All safety analyses will be conducted in this population
- *Pharmacokinetic Analysis Set:* all subjects who receive any amount of study drug will be included in the formal analysis of pharmacokinetic parameters providing they have at least one evaluable pharmacokinetic sample

Variables for Analysis:

Primary

- Safety parameters (i.e., changes in clinical signs and symptoms from physical exam, changes in clinical laboratory parameters, vital signs and adverse events [AEs])

Secondary

- Plasma concentrations of PP-001 and associated derived parameters (cohorts 1-3 only)

Safety analysis

The incidence of treatment-emergent AEs, serious AEs (SAEs), deaths and discontinuations of study drug due to an AE or SAE will be summarised by System Organ Class and Preferred Term according to the Medical Dictionary for Regulatory Activities, by relationship to study drug, and by severity. The incidence of potentially clinically significant vital signs will be summarised.

Pharmacokinetic analysis

The concentration of PP-001 in plasma will be measured in blood samples taken at Day 0 pre and post dose (0.5 h and 1h \pm 5 minutes after dosing) and on Day 8 and 19 at 0.5 h \pm 5 minutes after last instillation. Samples will be shipped to A&M GmbH, [name] for analysis. Only subjects of cohorts 1-3 will participate in pharmacokinetic sampling.

Table 1. Schedule of Assessments and Procedures (Cohorts 1-3):

Phase	Screening	Part I				Part II							Follow up
		Pre dosing	Post dosing	Telephone call ^a	Safety visits	Safety visits							
		Dosing Part I: *Day 0: administration on site				Dosing* Part II: *Day 8 and 9 (or more): administration on site *Day 10 – Day 19 (or more): self-administration							
Day	-14 to -2	0	0	1	2	6(+1)	8	9	10(+2)	15(±1)	19	21(±1)	28(±1)
Best corrected visual acuity (ETDRS)	X				X	X	X	X	X	X	X	X	X
Visual field (computerised, 30°)	X					X						X	
Intraocular pressure	X		X		X	X	X ^g	X ^g	X			X	
Slit lamp examination ^c	X	X	X		X	X	X ^b	X ^b	X	X	X	X	
Dilated fundoscopy ^d	X		X ^g		X	X	X ^g	X ^g	X			X	
Blood sampling for PK analysis		X	X ^e				X ^h					X ^h	
Fundus photography	X											X	
Amsler grid	X				X	X	X	X	X	X	X	X	
Urine pregnancy test		X				X							X
Medical and ophthalmic histories	X												
Vital signs ^f	X	X			X	X	X	X	X	X	X	X	
Physical examination ⁱ	X	X	X										X
Electrocardiogram	X												
Laboratory assessments	X											X	
Concomitant medication		←-----→											
Adverse events		←-----→											
Evaluation of ocular discomfort		X	X	X	X	X	X	X	X	X	X	X	X
Subject diary of instillation times, AEs and CM		X	X	X	X	X	X	X	X	X	X	X	X

ETDRS: Early Treatment of Diabetic Retinopathy Study; PK: Pharmacokinetic; AE: adverse event; CM: concomitant medications

a. Standardized questions including (but not limited to): pain, blurred vision, change in visual acuity, redness of the eye

b. Examination will be performed after each administration of study drug

c. Conjunctiva (redness standard scales), cornea, anterior chamber, lens

- d. Including slit lamp biomicroscopy of the fundus
- e. Day 0 blood samples will be taken 30 minutes and 1 hour after instillation
- f. Blood pressure and heart rate
- g. Examination will be performed after administration of final study drug
- h. Day 8 and Day 19 blood samples will be taken 30 minutes after last instillation of the day
- i. Height and weight at screening only

* Dosing in part II should be started earliest Day 8 after first administration in part I

Table 2. Schedule of Assessments and Procedures (Cohort 4):

	Screening	Safety visits						Follow up
		Dosing: *Day 0 and 1: first administration on site *Afterwards: self-administration until day 11						
Day	-14 to -2	0	1	2(+2)	7(±1)	11	13(±1)	20(±1)
Best corrected visual acuity (ETDRS)	X	X	X	X	X	X	X	X
Visual field (computerised, 30°)	X						X	
Intraocular pressure	X	X ^b	X ^b	X			X	
Tear film osmolarity	X	X ^b	X ^b	X	X	X	X	X
Slit lamp examination ^c	X	X ^b	X ^b	X	X	X	X	X
Tear film break up time	X	X ^b	X ^b	X	X	X	X	X
Corneal staining with fluorescein	X	X ^b	X ^b	X	X	X	X	X
Conjunctival staining using lissamine green	X	X ^b	X ^b	X	X	X	X	X
Dilated fundoscopy ^d	X	X ^b	X ^b	X			X	
Amsler grid	X	X	X	X	X	X	X	
Urine pregnancy test	X	X						X
Medical and ophthalmic histories	X							
Vital signs ^e	X	X	X	X	X	X	X	
Physical examination ^f	X							X
Electrocardiogram	X							
Laboratory assessments	X	X ^g					X	
Concomitant medication		←-----→						
Adverse events		←-----→						
Evaluation of ocular discomfort ^a		X	X	X	X	X	X	X
Ocular Surface Disease Index	X					X		
Subject diary of instillation times, AEs and CM		X	X	X	X	X	X	X

ETDRS: Early Treatment of Diabetic Retinopathy Study; AE: adverse event; CM: concomitant medications

a. Standardized questions including (but not limited to): pain, blurred vision, change in visual acuity, redness of the eye

- b. Examination will be performed after administration of study drug
- c. Conjunctiva (Efron scale), cornea, anterior chamber, lens
- d. Including slit lamp biomicroscopy of the fundus
- e. Blood pressure and heart rate
- f. Height and weight at screening only
- g. Alcohol and drug screen only

LIST OF ABBREVIATIONS AND DEFINITIONS OF TERMS

Abbreviation	Definition
AE	Adverse event
AKC	Adenoviral keratoconjunctivitis
AUC	Area under the plasma concentration time curve
AUC _{0-∞}	Area under the curve from time 0 to infinity
AUC ₀₋₂₄	Area under the curve from time 0 to 24 h post-dose
BP	Blood pressure
CS	Clinically significant
Cmax	Maximum plasma concentration
DHODH	Dihydroorotate dehydrogenase
DSMB	Data safety monitoring board
EAU	Experimental autoimmune uveitis
ECG	Electrocardiogram
eCRF	Electronic case report form
ETDRS	Early Treatment of Diabetic Retinopathy Study
EU	European Union
FIH	First in human
GCP	Good clinical practice
GMP	Good manufacturing practice
HAV	Human adenovirus
HR	Heart rate
HSA	Human serum albumin
IC ₅₀	Half-maximal inhibitory concentration
ICH	International Conference on Harmonisation
IEC	Independent ethics committee
IFN-γ	Interferon gamma
IL-17	Interleukin 17
IP	Investigational product (PP-001)
ITT	Intent-to-treat
MedDRA	Medical Dictionary for Regulatory Activities
NCS	Not clinically significant
NIU	Non-infectious uveitis
OECD	Organisation for Economic Co-operation and Development
QA	Quality assurance
SAE	Serious adverse event
SRM	Study reference manual
t _½	Terminal phase half-life
TEAE	Treatment-emergent adverse event
t _{max}	Time to maximum concentration

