Pharmacokinetic and metabolic parameters have been evaluated *in vitro* and *in vivo* in various species.

PP-001 exhibited strong *in vitro* plasma protein binding (>99.9% binding) and high metabolic stability after incubation with human liver microsomes. Inhibition potential towards human Cytochrome P450 (CYP450) enzymes was detected, but considered insignificant due to a very low systemic PP-001 exposure after topical ocular administration.

Single and multiple administrations of different PP-001 eyedrop formulations (clinical and development formulation) in rabbits resulted in maximum systemic exposure in the low ng/ml range. Maximum PP-001 concentrations in plasma ranged between 9 ng/ml after a single dose of 105 µg PP-001 (clinical formulation) and 23 ng/ml after multiple doses of PP-001 (development formulation; one eye per animal treated 4 times daily over 14 days; 420 µg PP-001 total daily dose).

Ocular tissue concentrations following single and multiple instillations of PP-001 eyedrop formulations were highest in conjunctiva followed by cornea. After a single dose (105 and 91 µg PP-001 per drop for clinical and development formulation, respectively), maximum tissue concentrations ranged between 1.3 ± 0.1 µg/g (clinical formulation) and 12.4 ± 4.9 µg/g (development formulation) in conjunctiva. In cornea, maximum tissue concentration ranged between 0.4 ± 0.04 µg/g (clinical formulation) and 9.4 ± 2.0 µg/g (development formulation).

Multiple topical instillations (4 drops daily over 4 days, 365 µg PP-001 total daily dose per eye, development formulation) resulted in maximum tissue concentrations of 9.2 ± 3.2 µg/g in conjunctiva and 9.3 ± 3.0 µg/g in cornea. No tissue accumulation following multiple dosing over four days compared to a single dose was detected in conjunctiva whereas a slight accumulation

was determined in the corneal tissue (1.9 fold). Half-life of PP-001 after multiple dosing over four days in rabbits was 2.7 hours in conjunctiva, 9 hours in cornea and 1.4 hours in peripheral blood.

PP-001 does not elicit ocular melanin binding properties as shown in an *in vivo* ocular distribution study comparing PP-001 tissue content in pigmented and non-pigmented rats.

Non-Clinical Safety and Toxicology

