2.4 Secondary Endpoints

- The concentration of PP-001 in plasma at predose, postdose (30 min and 1h \pm 5 minutes after dosing), day 8 and day 19 (30 min \pm 5 minutes after last dosing of the day) will be determined.
- Pharmacodynamic parameters relating to the eye as assessed through:
 - Best corrected visual acuity
 - Visual field
 - Intraocular pressure
 - Slit lamp examination
 - ad slit lamp examination: Conjunctival hyperemia according to the Efron scale (cohort 4 only)

- Dilated fundoscopy
- Fundus photography (cohorts 1-3 only)
- Amsler grid
- OSDI score (cohort 4 only)
- Tear film osmolarity (cohort 4 only)
- Tear film break up time (cohort 4 only)
- Corneal fluorescein staining (cohort 4 only)
- Conjunctival staining using lissamine green (cohort 4 only)

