5.2 Timing of Dosing and Dose Administration

Cohorts 1-3:

Subjects will receive IP on Day 0 (single dose) and then Days 8–19 (48 doses).

On Day 0, the IP dose will be administered in house by site staff. Staff will administer a single drop of IP into one eye.

On Day 8 and 9, the IP doses will be administered in house by site staff. Staff will administer a single drop of IP into one eye four times throughout the dosing day separated by at least 4 hours.

On Days 10–19, the IP will be self-administered. Subjects will administer a single drop of IP into one eye four times throughout each dosing day separated by at least 4 hours.

Cohort 4:

Subjects will receive IP on Days 0-11 (24 doses).

On Day 0 and 1, the first instillation will be performed in house by site staff. Staff will administer a single drop of IP into one eye. At all following time points, the IP will be self-administered. Subjects will administer a single drop of IP into one eye two times throughout each dosing day separated by at least 8 hours.

Since only one randomly assigned eye will be treated, subjects will be handed out a bottle of topical lubricants (Genteal HA, Laboratoires Thea, France) as standard of care treatment for the control eye as needed. Subjects will be instructed to document instillation dates and times for Genteal HA eye drops in the diary.

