6.2 Sample Collection for Pharmacokinetic Analysis

6.2.1 Plasma Sample Collection

Blood samples for pharmacokinetic analysis of PP-001 in plasma following dosing will be collected at the times outlined in the Time and Events table (Table 1).

Blood samples will be collected into tubes containing tri-potassium ethylenediaminetetraacetic acid, immediately chilled on crushed ice, and then centrifuged at approximately 2000 g for approximately 10 minutes at +4°C to separate plasma. Following centrifugation, plasma specimens will be transferred as 2 equal aliquots (aliquot A and B) in microtubes. Plasma tubes have to be

labelled at least with the following information: PP-001-1101, subject number, sample ID (day 0, predose; day 0, 30 min; day 0, 60 min; day 8; day 19), aliquot ID (A or B). Promptly following centrifugation, plasma samples will be immediately frozen and stored at -20°C or cooler until transported. The total time from blood withdrawal to storage of plasma at -20°C should not exceed 60 minutes. The primary samples (aliquot A) will be transferred on dry ice to A&M GmbH for analysis.

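### Table 1 marks the end-of-dosing PK sample under Day 21(±1) although its footnote and the rest of the plan say Day 19, and the Day 19 sampling window rests on a self-reported drop time

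*Protocol*

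**What the plan says.** **The schedule.** In protocol Table 1 (Cohorts 1-3), the row "Blood sampling for PK analysis" has a mark with footnote h under Day 8 and a second one under Day 21(±1). Its Day 19 cell is empty, although other assessments are scheduled on Day 19.

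**The text.** Footnote h reads "Day 8 and Day 19 blood samples will be taken 30 minutes after last instillation of the day". Day 19 is also the time given in the synopsis, Sections 2.4, 9.4.2 and 9.7, and SAP Section 1.3.2. The synopsis, Sections 2.4 and 9.4.2 and the SAP add a tolerance of ±5 minutes. Section 6.2.1 says that samples "will be collected at the times outlined in the Time and Events table (Table 1"), and the same section prescribes tube labels that include day 19 and no day 21.

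**The dosing.** Treatment ends on Day 19. Section 5.2 has staff give every drop on Days 8 and 9, then states "On Days 10–19, the IP will be self-administered", four times a day at least 4 hours apart. Section 5.6 has the subject record those times on a diary card, which staff transcribe into the eCRF.

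**The analysis.** SAP Section 5 only lists plasma concentrations. Protocol Section 9.7 also promises graphs and summaries by time point, day and treatment group.

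**The concern.** Two separate problems affect the same sample.

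First, the schedule that Section 6.2.1 makes operative puts the sample in a visit at which it cannot meet its own definition, because there is no instillation on Day 21. A site working from the grid could draw the blood with the Day 21 laboratory tests. The only label available for that tube says day 19, so the mistake need not be visible afterwards.

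Second, correcting the column does not secure the timing. A ±5-minute window is set around a drop that the subject instils, and nothing requires that drop to be given or witnessed at the site. On Day 8, by contrast, staff give every drop.

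At stake is the only plasma sample taken after more than one day of repeated dosing. Low systemic exposure is central to the risk argument in Sections 3.1.1 and 3.2. A late draw could be read as support for that argument when its timing made a low value likely.

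**Working it through.** Neither document calculates anything for this sample, so there is no planned figure to reproduce.

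**1. Position of the mark.** The Day header and twelve assessment rows of Table 1 were aligned cell by cell; each has 14 cells. The PK marks fall at Day 0 before dosing, Day 0 after dosing (footnote e), Day 8 (h) and Day 21(±1) (h). Neighbouring rows align sensibly. In Part II, footnotes b and g fall on Days 8 and 9, when staff give the drops. Slit lamp, Amsler grid and vital signs have separate marks for Day 19 and Day 21(±1).

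**2. Earliest time of the last Day 19 drop.** Four drops at least 4 h apart leave three intervals: 3 × 4 = 12 h after the first drop. The sample is due 30 ± 5 minutes after that.

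**3. What a late draw would show.** Inputs:
- Half-life h: Section 1.3 gives, for rabbits, "9 hours in cornea and 1.4 hours in peripheral blood". I use 1.4 h as the plasma value and 9 h as a deliberately slow case. No human plasma half-life is given, so applying either to humans is an assumption.
- Starting level: 23.1 ng/ml, the rabbit maximum after repeated topical dosing at 3.0 mg/ml (Section 3.1.1).
- Limit of detection: 10 ng/mL (Section 3.2).

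The fraction left t hours after the last drop is 0.5^(t/h), and the level is 23.1 × that fraction.

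| t | h = 1.4 h: half-lives, fraction, ng/ml | h = 9 h: half-lives, fraction, ng/ml |
|---|---|---|
| 0.5 h (as planned) | 0.4, 78%, 18 | 0.1, 96%, 22.2 |
| 4 h | 2.9, 14%, 3.2 | 0.4, 73%, 17.0 |
| 24 h | 17.1, 0.0007%, 0.0002 | 2.7, 16%, 3.6 |
| 48 h | 34.3, 5e-11, 1e-9 | 5.3, 2.5%, 0.57 |
| 72 h | 51.4, 3e-16, 8e-15 | 8.0, 0.4%, 0.09 |

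Day 21(±1) corresponds to about 24 to 72 h if the draw and the last drop share a clock time, hence 24/9 = 2.7 to 72/1.4 = 51.4 half-lives. A morning draw on Day 20 after an evening drop could come at about 12 h. In the slow case that still gives 23.1 × 0.5^(12/9) = 9.2 ng/ml, just under the limit.

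The level reaches 10 ng/ml at h × log2(23.1/10) = h × 1.208, that is 1.7 h for h = 1.4 h and 10.9 h for h = 9 h. A Day 19 draw at 4 h instead of 0.5 h would therefore read 1 − 0.5^(3.5/1.4) = 82% lower in the fast case and become undetectable. In the slow case it would read 1 − 0.5^(3.5/9) = 24% lower and stay detectable.

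**The case against.** **Day 19 is the dominant reading.** This stands. The footnote on the misplaced mark names Day 19, the instruction cannot be carried out on Day 21, and the tube label says day 19. A reader might infer that samples were drawn on Day 21; the documents do not show that any were.

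**The table was read from a PDF.** A shifted cell cannot be fully excluded. The pregnancy-test mark also disagrees with its text: Day 6(+1) in Table 1, Day 8 in Section 6.10. The consistent cell counts make a shift unlikely, but the sponsor should first look at the printed table.

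**Self-administered does not mean off site.** This also stands. There is a Day 19 visit at which the last drop could be instilled, and Section 6 asks for actual procedure times. Section 5.2 does not contradict the sampling time either, since Day 8 uses the same spacing and accepts a late draw. The gap is narrower: nothing requires or documents an observed drop.

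**The sample adds little on accumulation.** If the same drop times are kept each day and elimination is first-order, the Day 8 sample after the fourth drop is a fraction 1 − 0.5^(24/h) of steady state. That is essentially 100% for h = 1.4 h and 1 − 0.157 = 84% for h = 9 h. This limits the loss. It rests on the same borrowed half-lives, however, and the Day 19 sample is the only one that could check them in humans after 12 days.

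**The schedule correction comes late.** PK sampling is confined to Cohorts 1-3. SAP Section 2.11 says that recruitment began in November 2018, that Cohort 3 was stopped prematurely, and that the study restarted with Cohort 4. Nothing says Cohort 3 resumed. The correction is then largely documentary, but the analysis step remains open because SAP Section 2.1 plans one final analysis after database closure.

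**Conclusion.** The contradiction is in the current text and should be reconciled, and the ±5-minute window on Day 19 is not secured. Under rabbit half-lives of 1.4 to 9 h, a Day 21(±1) draw falls about 3 to 51 half-lives after the last drop and is expected to be below 10 ng/mL in every case computed.

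Three stronger readings are tempting and are not supported:
- That no drug would remain. The calculation supports only that no detectable drug is expected, and it uses rabbit values.
- That a low result would be due to timing alone. Section 3.2 expects systemic exposure close to or below the limit of detection, so a correctly timed sample may also be undetectable.
- That 18 actively treated subjects are affected. That is the planned number (3 × 6); with Cohort 3 stopped early it may be smaller.

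The reach is one sample for a secondary endpoint that the SAP only lists. The point merits correction because the remedy in the analysis is nearly free. It does not undermine the primary safety assessment.

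**What to change.** **Protocol.** After checking the printed table, move the footnote-h mark from the Day 21(±1) column to Day 19. For any subject still to be sampled, add a sentence to Section 6.2.1 saying how the time of the instillation before the Day 19 sample is verified. For example, the subject instils that drop during the Day 19 visit and staff record the clock time.

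**SAP.** For subjects already sampled, add to Listing 3.1 the actual sampling date and the hours since last instillation, derived from eCRF and diary times. Flag samples outside 30 ± 5 minutes. Leave flagged samples out of any Day 19 summary produced under protocol Section 9.7, but keep them in the listing. State that Day 19 dose times are self-reported where they were not observed.

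**Cost.** One table correction, one sentence, and the added listing columns, of which only the elapsed time has to be derived. No extra blood draw or visit is needed. The downside, for future subjects only, is a constraint on when the Day 19 visit is held, because the fourth drop comes at least 12 h after the first.
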